10.2.2 Adverse (Drug) reactions

According Directive 2001/20/EC adverse (drug) reactions (ADR) are all untoward and unintended responses to an investigational medicinal product related to any dose administered.

The definition implies a reasonable possibility of a causal relationship between the event and the investigational medicinal product (IMP). This means that there are facts (evidence) or arguments to suggest a causal relationship. The definition covers also medication errors, misuse and abuse of the product.

10.2.3 Serious adverse events (SAEs)

A SAE is any untoward medical occurrence or effect that at any dose:

- results in death;
- is life threatening (at the time of the event);
- requires in-subject hospitalisation or prolongation of existing inpatients' hospitalisation, unless it was a planned hospitalization, for instance for an elective surgery;
- results in persistent or significant disability or incapacity;
- is a congenital anomaly or birth defect;
- Is an important medical event that may jeopardize the subject or may require medical intervention to prevent one of the outcomes listed above..

Medical and scientific judgment should be exercised in deciding whether an AE is serious in other instances, such as an important medical event that may not be immediately life-threatening or resulting in death, or a hospitalisation that may jeopardize the subject or require intervention to prevent one of the above outcomes. Elective surgery for pre-existing conditions as noted in the CRF will not be included as SAE, unless the surgery is triggered by unexpected worsening of the clinical condition.

All SAEs will be reported by the investigator to the Accelovance Pharmacovigilance (PV) within 24 hours of first knowledge of the investigator or its team. All SAEs will be reported by submitting a completed SAE Report Form. Whenever possible, diagnoses should be given when signs and symptoms are due to a common etiology. It is critical that the information provided on the sponsor's SAE Report Form matches the information recorded in AE eCRF for the same event. In addition, the same information is to be recorded in the source documents.

PV will notify the sponsor of all SAE's within 24 hours of its initial receipt.

The CIOMS prepared by PV will be shared with sponsor for review and approval.

Pregnancy screening and handling is not applicable in this study as all subjects are 65 years or older.

10.2.4 Suspected unexpected serious adverse reactions (SUSARs)

Adverse reactions are all untoward and unintended responses to an investigational product related to any dose administered.

Unexpected adverse reactions are SUSARs if the following three conditions are met:

1. the event must be serious (see chapter 10.2.2);
2. there must be a certain degree of probability that the event is a harmful and an undesirable reaction to the medicinal product under investigation, regardless of the administered dose;

3. the adverse reaction must be unexpected, that is to say, the nature and severity of the adverse reaction are not in agreement with the product information as recorded in the SPC for an authorised medicinal product;

All serious and unexpected adverse reactions that are possibly, probably or definitely related to IMP are subject to expedited reporting to Regulatory Authorities and Ethic Committees, in accordance with ICH guidelines for GCP and the EU Directive 2001/20/EC and applicable local regulations.

SUSARs that are fatal or life-threatening must be reported as soon as possible and in any case no later than 7 calendar days after knowledge by PV/sponsor of such a case, and that relevant follow-up information is subsequently communicated within an additional eight days.

All other suspected serious unexpected adverse reactions shall be reported to the competent authorities concerned and to the IRB/IEC concerned as soon as possible but within a maximum of 15 calendar days of first knowledge by PV/sponsor.

PV will report any SUSARs on behalf of the sponsor to the IEC/CA according to local requirements. The IRB/IEC should receive the following SUSARs expeditedly:

- SUSARs that have arisen in the clinical trial that was assessed by the accredited ethical committee;

10.3 Annual safety update report

In addition to the expedited reporting of SUSARs, once a year throughout the clinical trial, a safety report will be submitted to the accredited ethical committee, competent authority and ethical committees & competent authorities of the concerned Member States.

This safety report will comprise a line listing of all SAEs, along with an aggregated summary table of all reported SAEs and other events of special interest (see 9.1.1.a), ordered by organ system.

10.4 Follow-up of adverse events

All AEs will be followed until they have abated, or until a stable situation has been reached; last potential follow up is at V10. Depending on the event, follow up may require additional tests or medical procedures as indicated, and/or referral to the general physician or a medical specialist.

10.5 Monitoring

Clinical trial management and monitoring will be performed by Curve Clinical. In order to ensure the clinical trial is managed and conducted properly Curve Clinical will:

- Set up workflows, timelines, project specific procedures and tracking tools;
- Monitor timelines and milestones on an ongoing basis and communicating the project status to the project team throughout the duration of the entire project;
- Conduct regular team meetings to discuss project status, activities, address issues, coordination of project specific trainings;
- Maintain regular contact with principal investigators;

- Provide status reports to principal investigator, regular site contacts, back-up according to agreed project structures;
- Provide weekly internal status reports to senior Curve Clinical staff;
- Maintain files according to the Standard operating procedures (SOPs);
- Supporting the site with protocol and study related questions;
- Supporting the study sites with patient visit coordination and patient follow up;
- Initiate actions to address project issues.

During the study, the monitor/clinical research associate will visit the investigational site regularly to check the completeness of patient records, the accuracy of entries in the eCRF, the adherence to the protocol and to GCP, the progress of enrollment, and to ensure that study drug is being stored, dispensed, and accounted for according to specifications. The monitor/clinical research associate is capable of reading the local language as well as being fluent in English. Key trial personnel must be available to assist the monitor during these visits. The investigator must maintain source documents for each patient in the study, consisting of case and visit notes (hospital or clinic medical records) containing demographic and medical information, laboratory data and the results of any other tests or assessments. All information on eCRFs must be traceable to these source documents in the patient's file. Data not requiring a written or electronic record will be defined before study start and will be recorded directly in the eCRFs, which will be documented as being the source data. The investigator must also keep the original of the signed informed consent form. The investigator must give the monitor access to all relevant source documents to confirm their consistency with the CRF entries. Curve Clinical monitoring standards require full verification for the presence of informed consent, adherence to the inclusion/exclusion criteria, documentation of SAEs, and the recording of data that will be used for all primary and safety variables.

11. STATISTICAL ANALYSIS

11.1 Primary study outcome(s)

Benefit

The two primary outcomes for benefit are RA disease activity and progression of joint damage. Disease activity is operationalized as DAS28. This index comprises a formula that includes 28 tender and swollen joint counts, general health (GH; patient assessment of disease activity; Likert scale from 0-10 recoded to 0-100, with 0=best, 100=worst), plus levels of ESR (mm/h)). For calculation of DAS28, please see appendix C. Damage progression will be evaluated by the total Sharp/van der Heijde damage score of hands and forefeet (appendix D).

Primary analysis: DAS28

The DAS28 is a continuous variable. We will compute the “time averaged DAS28” based on the trajectories over time for each individual, as part of the repeated measures in the longitudinal design. Observations are included in the follow up time until end of trial or the occurrence of a protocol violation (i.e., GC co-interventions as outlined in section 7.2).

The term ‘repeated measures’ refers to data with multiple observations on the same sampling unit; in this case, the multiple observations are taken over time (10 visits) in 450 RA patients. To address the issue of covariation between measures on the same unit, linear mixed models will be fitted because they permit the covariance structure to be incorporated into the statistical model. After modelling the covariance structure, inference about fixed effects proceeds essentially as when using simple Analysis of Covariance (ANCOVA); i.e., enabling estimation of group effects “averaged over time” measured in DAS28-units. Using repeated-measures mixed models we will analyse mean trajectories in continuous end points. The model will include treatment (group), and the multiple stratification variables (participating study site, prior exposure to GC, and concurrent start of other anti-rheumatic therapy) as fixed effects, with the baseline value of the relevant variable as a covariate.

Secondary analyses: DAS28

Change in DAS28 over the first 3 months of the trial (when the chance of co-intervention is least) will be compared between the treatment groups by ANCOVA, adjusting for the level at baseline. In secondary analyses, observations in patients after the protocol violation will be included in the analysis described above.

Damage progression will be evaluated by the change in total Sharp/van der Heijde damage score of hands and forefeet. It is known that this variable has a positively skewed distribution. Cumulative probability plot with the distribution of change in total Sharp/van der Heijde score from baseline to two-year follow-up will be applied as well as a non-parametric test (the Mann-Whitney test) to compare intervention and control groups.

Harm

The primary outcome variable for harm is operationalized as a binary variable with two categories (0= no adverse event, 1= at least one adverse event of special interest (see 9.1.1.a). This variable will be presented as a proportion. A chi-square test will be used to test for differences between the proportion of adverse events in intervention and control groups.

Secondary analyses:

A logistic regression model with harm as dependent variable will be fitted in order to adjust for potential factors that may alter the probability of AEs (as explained above for benefit). In addition absolute incremental risk and relative risk will be calculated for all major events, with confidence intervals.

Analysis strategy:

- One-sided significance levels (alpha=0.05); asymmetric null hypotheses: this approach increases the chance of rejecting the null hypotheses compared to standard two-sided testing. This results in a higher chance of declaring benefit (justified in view of scientific knowledge and the pragmatic trial design), but also a higher chance of declaring harm (to guard against the limited power of the study to detect harm).
 - confirmation of benefit: on the basis of the trial data we expect to reject the null hypothesis of GC (added to standard of care) yielding similar effectiveness compared to placebo (H_0); the alternative (H_1) hypothesis is that GC yields better effectiveness;
 - demonstration of absence of harm: we expect NOT to reject the null hypothesis that GC yields similar side effects; see 4.4 for considerations of the 95% non-inferiority confidence bound.
 - In case the trial detects a difference in AEs favoring the GC group, the superiority of GC will be tested in a secondary analysis.

For the interpretation of increases in the occurrence of AE of special interest that did not reach significance we will use the suggestions of the GRADE (Grades of Recommendations, Assessment, Development, and Evaluation) Working Group ([Guyatt 2012](#)), upper limit of one-sided 95% confidence limit (CL):

1. > 1.3 : GC associated with a trend towards greater occurrence;
2. ≤ 1.2 : GC appears to have little effect on the occurrence;
3. > 1.2 and ≤ 1.3 : results failed to demonstrate or exclude a greater occurrence.

In the case of a numerical DECREASE in AE, a more stringent test for significance will be performed ($p < 0.025$).

For the interpretation of decreases in the occurrence of AE that did not reach significance:

lower limit of one-sided 95% CL:

1. < 0.7 : GC associated with a trend towards reduced occurrence;
2. ≥ 0.8 : appears to have little effect on the occurrence;
3. < 0.8 and ≥ 0.7 : results failed to demonstrate or exclude a reduced occurrence.

Economic evaluation

The economic evaluation will comprise a cost-effectiveness and a cost-utility study. The evaluation will be performed according to the intention-to-treat principle and from a societal perspective. All direct medical and non-medical, and indirect costs were combined to calculate the costs per patient. Costs of hospitalization days, visits to medical specialists (direct costs), and help in the household (indirect costs) are valued with standard prices according to the Dutch manual for costing studies. Dutch prices will be used for all costs to keep costs comparable between countries. The unit prices of 2017 are used because most patients were

included in this year. The Dutch consumer price index will be used to account for inflation. Production losses will be valued using the friction cost method: only sick leave during a friction period (23 weeks) needed to replace a person is taken into account (indirect costs).

Outcome measures are time-averaged disease activity (DAS28) for the cost-effectiveness analysis and Quality-Adjusted Life Year (QALY) for the cost-utility analysis.

Confidence intervals (CI) for costs will be estimated with bias-corrected accelerated bootstrapping with 1000 iterations.

All patients will be included in the cost-utility and cost-effectiveness analyses according to the intention-to-treat principle. Missing data will be imputed with multiple imputation by chained equations (with predictive mean matching). Stepwise linear and logistic regression analyses will be used to examine which variables are associated with missingness, and such variables will be included in the multiple imputation model. The data are imputed as total costs or utility score or DAS28 per time point per treatment arm (prednisolone or placebo). The imputed datasets will be bootstrapped with 5000 replications in order to estimate the uncertainty around the difference in costs and effects.

The imputed datasets will be bootstrapped with 5000 replications in order to estimate the uncertainty around the difference in costs and effects. The incremental Cost-Effectiveness and Cost-Utility Ratios (ICER and ICUR) will be calculated by dividing the difference between the mean costs per treatment group by the difference between the time-averaged disease activity per group and by the difference in QALYs per patient. The results will be graphically presented on a cost-effectiveness and cost-utility plane, and a cost-effectiveness acceptability curve will be constructed. This results in four different quadrants: two showing dominance of one treatment over the other, and two indicating a tradeoff between QALYs and costs.

Medication adherence

- Nonparametric and parametric comparisons between treatment groups where appropriate; one-sided significance levels ($\alpha=0.05$)
- Handling of premature discontinuations, dropouts and missing data: each patient will contribute until moment of discontinuation (weighted by total time in trial)

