- To measure benefit, primary endpoints are a) signs and symptoms: the time-averaged mean value (estimated from linear mixed models) of the DAS28; b) damage progression: change from baseline after 2-years in total Sharp/van der Heijde damage score of hands and forefeet radiographs.
- To measure safety, the primary endpoint is the total number of patients experiencing at least one serious adverse event, or one clinical event related to the disease or its therapy.
- Other major outcomes are cost-effectiveness, cost-utility, and medication adherence.

Assessment takes place at varying intervals, and includes seven clinic visits and 3 assessments by telephone.

Nature and extent of the burden and risks associated with participation, benefit and group relatedness:

GLORIA is a pragmatic trial, with measurements that are almost all part of standard of care, and therefore there are no additional risks associated with these measurements. However, the intervention in this trial is that patients are randomized to either standard of care with low-dose GCs or standard of care without low-dose GCs for a duration of two years. It is known that GCs have strong favourable effects on disease activity, of which patients randomised to the control arm (placebo) cannot benefit. However, side effects of GCs are known as well, and patients in the experimental arm (prednisone 5 mg/day) might suffer from them. Although side effects predominantly occur when GC are used in high doses for long periods of time, elderly are more likely to suffer from adverse effects of the disease and its therapy than younger patients. However, elderly are underrepresented or even excluded from many clinical trials, so it is difficult to estimate their risk: this forms the rationale for the trial. To reduce risks, participants are monitored and patients with a low probability of benefit or with a high probability of harm will be excluded from participation to this trial. For the substudy to measure adherence through an innovative application, no additional risks are expected: if the application appears to be successful, patients randomised to the intervention can only benefit from it since it improves their medication adherence; in case the application is not successful, for patients not randomised to the application or for patients without a smartphone, no difference is expected with the 'normal' situation, in which patients do not have access to an adherence application.

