9.3.5 Efficacy assessments

Evaluation of joints and disease activity scores

An assessment of 44 joints for swelling and tenderness will be performed at baseline and after 24 months, assessment of 28 joints at 3, 6, 12 and 18 months. Joint swelling will be assessed as absent or present; joint Version 4.0 (12-Feb-2019)

tenderness will be graded semi-quantitatively from 0-3 for the 44 joint score (Ritchie Articular Index (RAI)) ([Ritchie DM 1968](#)) and as absent or present for the 28-joint score. Appendix B.

The DAS28 is a composite index taking into account the tenderness and swelling score of 28 joints, laboratory ESR, and the global assessment of disease activity. The DAS28 has a range of 0 to 9.4, in which levels below 3.2 represent low disease activity, and levels equal or greater than 3.2 represent high disease activity. The EULAR response and ACR response are rated according to appendix C.

Damage progression of the joints in the hands and forefeet will be evaluated by the total Sharp/van der Heijde damage score (appendix D).

Global disease activity

The physician will answer a question on global assessment of disease activity on a 21-point Likert Scale (at the time points indicated in Table 2; appendix F).

The patient will answer two questions in a similar way:

1. global assessment of disease activity (appendix E).
2. pain question: this question is part of the RA Impact of Disease (RAID) questionnaire, see appendix H.

Stiffness

Morning stiffness severity is assessed using a 21-point Likert Scale. In addition, morning stiffness duration in minutes is assessed. See appendix E.

(Modified) Health Assessment Questionnaire ((M)HAQ)

The (M)HAQ index is a patient completed questionnaire specific for RA to assess physical functioning. The full HAQ consists of 20 questions referring to 8 component sets: dressing/grooming, arising, eating, walking, hygiene, reach, grip, and activities. The MHAQ consists of 10 questions. Appendix GF.

Rheumatoid Arthritis Impact of Disease Questionnaire (RAID)

The RAID is a validated questionnaire assessing the seven most important domains of impact of RA on the patients, with a 21-point Likert Scale. See appendix H.

Cost questionnaire

Data about costs for health care and housekeeping, and sick leave in paid and unpaid work are collected with the cost questionnaire in appendix I.

Quality of life

The EQ-5D and the SF36 will be completed to assess QoL. They are added as appendix J and appendix K.

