## 1.4.2 Secondary endpoints

### *Benefit*

- WHO-ILAR core set of RA outcome measures, including patient and physician global assessment of disease activity, joint counts (swollen joints and tender joints), acute phase reactants (C-reactive protein (CRP) and erythrocyte sedimentation rate (ESR)) at 0, 3, 6, 12, 18, 24 and 27 months, and radiographs of hands and forefeet at 0 and 2 years.  
Remaining core set measures: pain and fatigue are part of the RAID questionnaire (see below), and physical function is assessed by the (m)HAQ.
- DAS44 – at 0 and 24 months
- DAS28 – at 3, 6, 12, 18, and 27 months
- Severity and duration of morning stiffness - at every study visit
- SF36 – The Short Form 36-item Health Survey, a questionnaire about quality of life (QoL) - at 0 and 24 months
- 57-symptom list – at 0 and 24 months
- RA Impact of Disease (RAID) tool – The RAID is a validated questionnaire assessing the seven most important domains of impact of RA on the patients: pain, functional disability assessment, fatigue, sleep, physical well-being, emotional well-being, coping. – at every study visit
- (Modified) Health Assessment Questionnaire ((m)HAQ) at every study visit
- RAPID3, calculated with the patient global assessment of disease activity, (m)HAQ and the question about pain from the RAID questionnaire, at every study visit
- Cost questionnaire at 0, 3, 6, 12, 18, 24, 27 months, including
  - Activity limitation
  - Work disability (for those holding a paid job)
- Utility/Quality-adjusted life years (QALY): Euro-QoL in 5 dimensions (EQ-5D) - at every study visit

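### The cost-utility ratio has no stated adjustment for baseline EQ-5D utility, which costs precision; the source and direction of the DAS28 effect also need stating

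*Protocol*

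**What the plan says.** The economic evaluation in Protocol 11.1 names its two effects: "Outcome measures are time-averaged disease activity (DAS28) for the cost-effectiveness analysis and Quality-Adjusted Life Year (QALY) for the cost-utility analysis". The cost-effectiveness ratio is obtained "by dividing the difference between the mean costs per treatment group by the difference between the time-averaged disease activity per group", and the cost-utility ratio by dividing the same cost difference "and by the difference in QALYs per patient". Missing totals are multiply imputed per time point and per arm, and the imputed datasets are bootstrapped 5000 times. No regression model, covariate or order of subtraction is given for either ratio. The quadrants of the plane are described as "two showing dominance of one treatment over the other, and two indicating a tradeoff between QALYs and costs", with no matching description for DAS28.

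Three other places bear on this:

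- The SAP's list of secondary benefit endpoints has "Utility/Quality-adjusted life years (QALY): Euro-QoL in 5 dimensions (EQ-5D) - at every study visit", so a baseline utility exists for adjustment.
- The Protocol summary defines the clinical endpoint as "the time-averaged mean value (estimated from linear mixed models) of the DAS28", and the mixed model in Protocol 11.1 is fitted "with the baseline value of the relevant variable as a covariate".
- SAP 1 and SAP 1.4.1 leave the details of the economic evaluation to a separate analysis plan, which is not among the documents.

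**The concern.** Baseline utility usually predicts later utility, and so predicts QALYs over two years. Protocol 9.2 minimises on site, prior glucocorticoid exposure and concurrent start of other antirheumatic therapy. It does not minimise on utility or DAS28. Any chance difference in baseline EQ-5D therefore passes into an unadjusted QALY difference, and the variation in QALYs that baseline explains stays in the standard error. The clinical DAS28 analysis removes this by adjusting for baseline. The stated cost-utility estimator has no equivalent step.

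Cost-effectiveness is part of the first primary objective (Protocol 4.1). QALY differences between active treatment and placebo on top of standard care may be small, so the precision of that denominator matters.

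There is a second, smaller point. A lower DAS28 is better (Protocol 9.3.5: "in which levels below 3.2 represent low disease activity"), whereas planes and acceptability curves are normally read with more effect as better. The text should say which way the DAS28 difference is taken.

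**Working it through.** The documents give no power, standard error, ratio or threshold for the economic evaluation, so there is no figure of the plan's own to reproduce.

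**Inputs.** From the documents: 225 patients per arm (Protocol 6.4), and a DAS28 contrast of -0.52 from the 5 mg prednisone trial cited there (-1.15 minus -0.63). Assumed: utility SD 0.22, two-year QALY SD 0.38, correlation r between baseline utility and QALYs of 0.5 to 0.7, and a cost difference of +1,000 euro for the sign illustration.

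**1. Precision of the QALY difference.**

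- Unadjusted SE = 0.38 × sqrt(2/225) = 0.0358.
- Adjusted SE = 0.0358 × sqrt(1 − r²).

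| r | sqrt(1 − r²) | Adjusted SE | Reduction in SE | Equivalent extra patients, 1/(1 − r²) − 1 |
|---|---|---|---|---|
| 0.5 | 0.866 | 0.031 | 13% | 33% |
| 0.6 | 0.800 | 0.029 | 20% | 56% |
| 0.7 | 0.714 | 0.026 | 29% | 96% |

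The percentage columns depend only on r. The assumed SDs affect only the absolute standard errors.

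**2. Carry-over of a chance imbalance.**

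- SE of the baseline utility difference = 0.22 × sqrt(2/225) = 0.0207.
- Expected shift in the unadjusted QALY difference for a one-SE imbalance, at r = 0.6: 0.6 × (0.38/0.22) × 0.0207 = 0.0215 QALY.
- A wider range, taking the shift as 2 years × r × SD × sqrt(2/225) with utility SD 0.15 to 0.30 and r 0.3 to 0.7: 2 × 0.3 × 0.0141 = 0.008 up to 2 × 0.7 × 0.0283 = 0.040 QALY.

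Divided by the SE of the QALY difference, the one-SE shift equals r by algebra. It is another view of step 1 and not a separate finding.

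**3. Which DAS28 difference feeds the ratio.** The summary and the clinical part of Protocol 11.1 point to a mixed-model estimate adjusted for baseline. The economic part of 11.1 describes DAS28 imputed per time point and arm, bootstrapped, and then differenced between groups. It does not say that the mixed model is fitted in each replicate. If it were not, a 1.96-SE baseline imbalance would move the difference by r × 1.96 × SD × sqrt(2/225). With assumed baseline SD 0.8 to 1.3 and r 0.3 to 0.7, that is 0.04 to 0.17 points, or about 8.5% to 32% of 0.52.

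**4. Direction of the DAS28 effect (illustration).**

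- Effect taken as prednisolone minus placebo: 1000/(−0.52) = −1,923 euro per point, on the side of the plane usually read as less effective. Net benefit at 2,000 euro per point = 2000 × (−0.52) − 1000 = −2,040.
- Effect taken as points reduced: 1000/0.52 = +1,923 euro per point, on the more effective side. Net benefit = 2000 × 0.52 − 1000 = +40.

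The text of 11.1 fixes neither reading.

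**The case against.** The best defence is that nothing here is an error. Under randomisation the unadjusted QALY difference is unbiased on average, and the bootstrap reflects the sampling variation that comes from chance imbalance. That stands, and the point is confined to precision and to imbalance in the trial as realised.

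The second defence is that silence is not a decision. Baseline adjustment and axis direction are the kind of detail a separate economic plan would contain, and Protocol 11.2 lists QALYs among variables to be studied with mixed regression models. This also carries weight. However, 11.2 does not say that those models supply the cost-utility ratio, and the protocol does set out how the ratio is formed.

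The third is that the sizes rest on assumed SDs and correlations, and that only the QALY difference is examined. Correct: cost variation also drives the uncertainty of the ratio and was not assessed, so the 13% to 29% applies to the QALY difference alone.

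Two stronger readings are tempting, and the documents do not support them:

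- **That the DAS28 ratio has the wrong sign, so an effective drug is plotted as less effective.** SAP 4.8.1.1 writes its hypothesis as treatment minus control with benefit negative, and carrying that contrast over would produce this plot. But Protocol 11.1 gives no order of subtraction for the ratio, so reversal is only one possible reading.
- **That the DAS28 effect is unadjusted for baseline.** The protocol defines time-averaged DAS28 as a mixed-model estimate, and that model has baseline as a covariate. What is missing is a statement that this estimate is the one used in the ratio.

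**Conclusion.** The point holds as a modest improvement to the stated method. As written, the cost-utility denominator has no adjustment for a baseline utility that is collected and is not balanced by the minimisation. Adjusting would shrink the standard error of the QALY difference by about 13% to 29% if the baseline-QALY correlation is 0.5 to 0.7, and by less if it is weaker. It would also remove the expected carry-over of a chance imbalance, roughly 0.008 to 0.040 QALY per one-SE imbalance under the wider assumptions. No bias is shown, and no figure in the plan is contradicted. The source and direction of the DAS28 effect are matters for clarification. The whole conclusion is conditional on the separate economic plan, which may already settle all three.

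**What to change.** In Protocol 11.1 and the separate economic plan:

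1. Within each imputation and bootstrap replicate, estimate incremental QALYs by regression on arm, baseline EQ-5D utility and the stratification factors, and use that coefficient in the cost-utility ratio.
2. State that the cost-effectiveness ratio uses the baseline-adjusted time-averaged DAS28 difference, from a model with the covariates of the clinical analysis. Fit it in each replicate to the imputed intention-to-treat data, because the clinical primary analysis in Protocol 11.1 stops at a protocol violation and the economic evaluation does not.
3. For clarity, define cost as prednisolone minus placebo and the DAS28 effect as placebo minus prednisolone (points reduced), so that the plane and the acceptability curve read in the usual direction.

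This costs a few sentences and one regression per outcome in each replicate. All the variables are already collected, and nothing in trial conduct changes. If the economic plan already specifies these steps, it is enough to align the protocol text with it.
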